4.4 Subject Discontinuation Criteria

Subject participation in this study may be discontinued for any of the following reasons:

- withdrawal of informed consent;
- any clinical AE, laboratory abnormality, or other medical condition (including pregnancy) that indicates to the investigator that continued participation is not in the best interest of the subject;
- non-compliance with study procedures;
- termination of the study by the sponsor, United States (US) FDA, or other regulatory authorities; or
- lost to follow-up.

Protocol deviations should not lead to subject withdrawal unless they indicate a significant risk to the subject's safety or jeopardize the scientific integrity of the study.

A subject withdrawn from the study due to any AE or clinically significant abnormal laboratory test values will be evaluated by the investigator or other monitoring physician and will be treated and/or followed up until the symptoms or values return to

normal or acceptable levels, or until the subject is lost to follow-up, as appropriate in the opinion of the investigator.

4.5 Discontinuation Procedures

Subjects who are initially confirmed as eligible during screening but are deemed ineligible before enrollment (randomization) will be considered a “screen failure.”

If premature withdrawal from the study occurs for any reason, the investigator must determine the primary reason and record this information in the case report form (CRF). Subjects withdrawn or dismissed by the investigator after enrollment (Day 1) will undergo End of Study procedures as feasible.

4.6 Replacement Subjects

Subjects withdrawn from the study may be replaced at the discretion of the sponsor.

4.7 Concomitant Medications

Any concomitant medications taken from 30 days before Visit 1 (screening) through the end of study (or upon early termination) will be recorded.

Use of prescription or over-the-counter medications/supplements required to treat a non-exclusionary disease or condition are permitted at the discretion of the investigator, provided the medication in question would have no effect on interpretation of analyte values. In-clinic use of over-the-counter medications (e.g., acetaminophen, ibuprofen) is permitted at the discretion of the investigator as needed by subjects, provided the medication in question would have no effect on interpretation of analyte values.

5.0 Study Conduct

5.1 Procedures by Visit/Day

5.1.1 Visit 1 (Screening)

The following screening procedures will be completed within 30 days of subject enrollment:

- Verify age and identity with government-issued identification
- Explain study procedures and obtain signature on the informed consent form
- Review inclusion and exclusion criteria
- Document demographics (Demographics Questionnaire)
- Document tobacco/nicotine product-use history (Tobacco/Nicotine Product Use-History Questionnaire)
- Record medical history
- Measure vital signs
- Measure height, weight, and BMI
- Collect blood sample for clinical chemistry (at least 8 hours fasting), hematology (at least 8 hours fasting), serology, and serum pregnancy (all females only) tests
- Follicle-stimulating hormone test for postmenopausal females only
- Collect urine sample for urinalysis, drug and alcohol screening, and cotinine screening (exhaled breath test for alcohol is also acceptable)
- Review concomitant medications and AEs
- Electrocardiogram
- Physical examination
- Provide tobacco cessation information (Quit Assist™ website referral)

5.1.2 Visit 2: Day -1 Check-in

Subjects will return to the clinic for their second visit on Day -1, and the following procedures will be completed:

- Review inclusion and exclusion criteria
- Measure vital signs
- Collect urine sample for urine drug and alcohol screening (exhaled breath test for alcohol is also acceptable), urine pregnancy test (all females only)
- Product trial
 1. Subjects will use the products in an assigned order (A, B, C, D)

2. Subject will engage in brief product trial with each e-vapor product (i.e., ad libitum use for 10 minutes).
3. Trials of each e-vapor product will be separated by approximately 30 minutes (from the end of each product trial).
- Review concomitant medications and AEs
- Remind subjects of study restrictions

5.1.3 Visit 2: Day 1 through Day 4

Subjects will abstain from tobacco or nicotine use overnight and repeat the following procedures on Days 1, 2, 3 and 4:

- Measure vital signs
- Subjects will be randomly assigned to a product use schedule (section 5.3)
- Exhaled breath product-use session (1 test product per day for 4 days per randomization schedule)
 1. 10 sham puffs (empty cartridge and inactive battery)
 - 5-second puff duration, one puff every 30 seconds for 5 minutes (Note: All exhaled breath will be captured after the first puff to ~60 seconds after the last puff in Trapping Container 1 with a nose clip in place.) All puff durations will be documented.
 - Subjects will be instructed to inhale as they normally use EVPs and not to only mouth puff.
 - Subjects will also be instructed to make every attempt to exhale directly into the collection device and minimize leakage of the exhaled vapor in the ambient air.
 2. 10 puffs with assigned test product with fully charged standard battery (BVR2.3)
 - 5-second puff duration, one puff every 30 seconds for 5 minutes (Note: All exhaled breath will be captured after the first puff to ~60 seconds after the last puff in Trapping Container 1 with a nose clip in place.) All puff durations will be documented.
 - Subjects will be instructed to inhale the vapor as they normally use EVPs and not to only mouth puff.
 - Subjects will also be instructed to make every attempt to exhale directly into the collection device and minimize leakage of the exhaled vapor in the ambient air.
 3. At least 45 minutes without any tobacco or nicotine use

4. Cartridge (only test product cartridges) will be weighed within 90 minutes prior to the first 10 puffs. The cartridge will be weighed again after the first exhaled breath measurement and before the second exhaled breath measurement.
5. 10 sham puffs (empty cartridge and inactive battery)
 - 5-second puff duration, one puff every 30 seconds (Note: All exhaled breath will be captured after the first puff to ~60 seconds after the last puff in Trapping Container 2 with a nose clip in place.) All puff durations will be documented.
 - Subjects will be instructed to inhale as they normally use EVPs and not to only mouth puff.
 - Subjects will also be instructed to make every attempt to exhale directly into the collection device and minimize leakage of the exhaled vapor in the ambient air.
6. 10 puffs with the test product
 - 5-second puff duration, one puff every 30 seconds (Note: All exhaled breath will be captured after the first puff to ~60 seconds after the last puff in Trapping Container 2 with a nose clip in place.) All puff durations will be documented.
 - Subjects will be instructed to inhale the vapor as they normally use EVPs and not to only mouth puff.
 - Subjects will also be instructed to make every attempt to exhale directly into the collection device and minimize leakage of the exhaled vapor in the ambient air.
 - Weigh cartridge (test product only) again (within 90 minutes)
- Subject will be allowed to use new cartridges with fully charged (within 24hrs) “BVR2.3 Rev 05 batteries with topography v2” batteries ad libitum for the next 12 hours
- Measure weight of cartridges before and after ad libitum use (within 90 minutes)
- Record all cartridges used with each “BVR2.3 Rev 05 battery with topography v2”. All start and stop times with each cartridge and “BVR2.3 Rev 05 battery with topography v2” will be documented.
- Document likelihood of subject using product again (Use the Product Again Questionnaire) after each 12-hour ad libitum use session
- Review concomitant medications and AEs

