3.0 Summary of Study Design

3.1 Design

This is an open-label, 4-way crossover study designed to estimate the nicotine, glycerin, propylene glycol, menthol, formaldehyde, acetaldehyde, and acrolein levels in exhaled breath samples during use of four MarkTen® XL e-vapor products. The study will enroll approximately 32 adult e-vapor-using subjects. Each of the 32 subjects will provide two exhaled breath samples for all four test products. Subjects will make two visits to the site, one screening visit and one 4 day in-clinic visit to provide exhalation samples for four test products (one each day for 4 days). Subjects will also use their assigned test product ad libitum for 12 hours each day after the collection of exhaled breath samples. Subjects will be randomly assigned to a test product-use schedule at Visit 2, with one test product used per day.

At Visit 1 (screening), subjects (21–65 years of age) will complete vital sign assessment, serum pregnancy test (female subjects), urine drug/alcohol screen, the Demographics Questionnaire and Tobacco and Nicotine Product-Use History Questionnaire, blood hematology, clinical chemistry, urinalysis, a 12 lead ECG and complete a physical exam.

Approximately 32 eligible subjects (no more than 60% of either sex) may enroll into the study. Subjects will self-report that they have been using e-vapor products (EVPs) “some days” or “every day” for the past 30 days and for at least 4 out of the past 7 days.

- At Visit 2, upon arrival at the site, vital signs, urine pregnancy test (female subjects), and urine drug/alcohol screen will be conducted. After check in, subjects will engage in a brief product trial with each e vapor product following an assigned schedule (i.e., ad libitum use for 10 minutes) to get accustomed to using the products. Trials of each e-vapor product will be separated by approximately 30 minutes (from the end of each product trial). Subjects who react negatively (i.e., unwilling to use and/or cannot tolerate the product [e.g., experience adverse events (AEs) that will prevent them from continuing to use the product as judged by the investigator]) to any of the Nu Mark e-vapor products during the product trial will not continue in the study. Subjects will abstain from tobacco or nicotine use overnight, and on Day 1, subjects will be randomly assigned to a test product use schedule (1 Test Product per day for four

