5.3 Subject Randomization

On Day 1 (Visit 2), subjects (no more than 60% of either sex) will be randomized to one of four product-use order sequences in a 1:1:1:1 ratio (n = ~8 subjects from each subpopulation in each sequence: A B D C, B C A D, C D B A, D A C B). Subjects will also be randomized by sex.

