1.6 RANDOMIZATION

Each subject will be assigned to one of 4 test product sequences using a Williams design. The Williams design employs a Latin square, in which no test-product follows another specific test-product more than once in a given replication of the experiment (e.g., B will never follow A more than once in a 4x4 crossover design matrix). This property yields a balanced cross-over design wherein there is uniformity within both periods and sequences. In a balanced design, each of the test product types occurs the same number of times in each period and the number of subjects who receive test product type i in one period and test product type j in the next period is the same for all $i \neq j$ (Jones and Kenward 2003).

For this study, if the 4 test products are designated A, B, C, and D, the following 4x4 matrix (Table 2) represents one possible assignment of the 4 possible sequences to 4 different subjects. Thus the matrix represents one complete replication of the 4-period-4-sequence crossover experiment.

Table 2. Test Product Type Assignment in a Single Replication of a 4x4 Williams Crossover Design

Sequence	Test product type Assignment By Period			
	1	2	3	4
1	A	B	D	C
2	B	C	A	D
3	C	D	B	A
4	D	A	C	B

The randomizations will be done using a SAS macro program.^[6]

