1.7 STUDY PROCEDURES

At Visit 1 (screening), subjects (21–65 years of age) will complete vital sign assessment, serum pregnancy test (female subjects), urine drug/alcohol screen, the Demographics Questionnaire and Tobacco and Nicotine Product-Use History Questionnaire, blood hematology, clinical chemistry, urinalysis, 12 lead ECG and a physical exam.

Approximately 32 eligible adult subjects (no more than 60% of either sex) may enroll into the study. Subjects will self-report that they have been using EVPs “some days” or “every day” for the past 30 days and for at least 4 out of the past 7 days.

At Visit 2, upon arrival at the site, vital signs, urine pregnancy test (female subjects), and urine drug/alcohol screen will be conducted. After check in, subjects will engage in a brief product trial with each e vapor product following an assigned schedule (i.e., ad libitum use for 10 minutes) to get accustomed to using the products. Trials of each e-vapor product will be separated by approximately 30 minutes (from the end of each product trial). Subjects who react negatively (i.e., unwilling to use and/or cannot tolerate the product [e.g., experience adverse events (AEs) that will prevent them from continuing to use the product as judged by the investigator]) to any of the Nu Mark e-vapor products during the product trial will not continue in the study. Subjects will be given a facilitated “Use the Product Again Questionnaire” after the product trials. After all assessments are complete on Day –1, subjects will be randomly assigned to a test product use schedule (1 Test Product per day for four days). Subjects will abstain from tobacco or nicotine use overnight. On Day 1, Subjects will complete an

Statistical Analysis Plan

exhaled breath test product use session with their assigned test product. An exhaled breath test product use session will consist of the following: one sample with an empty cartridge and inactive battery [sham condition] and one sample using the assigned test product with all exhaled breath collected in one type of trapping container, followed by at least 45 minutes of rest, then the sham sample and same test product sample collection with a second type of trapping container. Each sample will consist of all the exhaled breath occurring during 10 puffs, each with 5 second puff duration (+/- 1 second), over approximately 5 minutes (one puff approximately every 30 seconds) collected in the respective sample collection container:

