2.1.3 Safety Population

The safety analysis set will include all subjects who used at least 1 of the study products.

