7.4 ADVERSE EVENTS

All AE data for the safety population will be coded (to the lowest-level term) by using the Medical Dictionary for Regulatory Activities (MedDRA, Version 17.1). AEs will be listed in by-subject data listings, including verbatim term (investigator terms from the case report form), preferred term, test product, severity, and relationship to test product. Summary tables of frequency counts of AEs will be provided by primary system organ class (SOC), preferred term, and test product. Frequency counts of AEs will also be summarized by severity and relationship to test product and overall.

A PEAE is defined as an adverse event that:

- Emerges during exposure to a test product, having been absent previously, or:
- Worsens in severity during sessions within visits 2, when the adverse event is continuous in duration.

The incidence (%) will be determined by calculating the number of subjects with at least 1 event and the percentage of subjects with PEAEs by preferred term. The

Statistical Analysis Plan

incidence of PEAEs will be reported as the number (percentage) of subjects with PEAEs by SOC and preferred term. A subject will be counted only once within a SOC and preferred term, even if the subject experiences more than one PEAE within a specific SOC and preferred term. A missing or unknown value for the assessment will be considered worst. The number (percentage) of subjects with PEAEs will also be summarized by maximum severity (mild, moderate, or severe). If a given subject had more than one PEAE mapped to the same PT, then that PEAE will be represented according to the corresponding maximal level of severity.

The number (percentage) of subjects with PEAEs will also be summarized by relationship to test product. If a given subject had more than one PEAE mapped to the same PT, then that PEAE will be represented according to the strongest relationship to study product. Test product-related PEAEs include those adverse events considered by the investigator to be “definitely”, “possibly”, “probably”, “unlikely”, or “not” related to test product usage. The number (percentage) of subjects with test product-related PEAEs will also be summarized by maximum severity (mild, moderate, or severe).

The number (percentage) of subjects with serious adverse events (SAEs) will be summarized by MedDRA, SOC, and preferred term for each test product group. A subject data listing of all SAEs will be provided.

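### SAP 7.4 does not clearly keep the Day -1 product trial, where product and trial position coincide, out of the by-product adverse event tables

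*Protocol*

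**What the plan says.** **The Day -1 trial.** Protocol 5.1.2 states: "Subjects will use the products in an assigned order (A, B, C, D". Protocol 3.1 describes the trial as "following an assigned schedule (i.e., ad libitum use for 10 minutes". On spacing, 5.1.2 says: "Trials of each e-vapor product will be separated by approximately 30 minutes (from the end of each product trial". A subject who cannot tolerate, or will not use, any one of the products goes no further.

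**Randomisation comes later in both documents.** Under Protocol 5.3, on Day 1, subjects "will be randomized to one of four product-use order sequences in a 1:1:1:1 ratio". SAP 1.7 places the step on Day -1, but only once that day's assessments are finished: "subjects will be randomly assigned to a test product use schedule". SAP 1.6 says of the Williams property: "This property yields a balanced cross-over design wherein there is uniformity within both periods and sequences".

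**Safety reporting.** SAP 2.1.3: "The safety analysis set will include all subjects who used at least 1 of the study products". Protocol 8.1 records adverse events from consent, with date and time of onset. SAP 7.4 counts an event as product-emergent if it first appears during exposure to a test product, or worsens within Visit 2, and Day -1 belongs to Visit 2. On layout, SAP 7.4 says: "Summary tables of frequency counts of AEs will be provided by primary system organ class (SOC), preferred term, and test product". It adds breakdowns by severity and relationship. Neither SAP 7.4 nor Protocol 9.6 splits adverse events by day or phase. Protocol 9.4 and SAP 4.1 hold a general rule to summarise by product and day; in SAP 4.1 it gives way wherever another layout is stated.

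**The concern.** The four randomised sequences balance order on Days 1-4 only. On Day -1, Product A is always tried with no earlier study product, and Product D always follows the other three. If events from that phase enter the by-product tables, three things follow:

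- Part of each product's incidence comes from a phase in which product and position cannot be separated.
- The percentage no longer refers to one exposure. It combines a 10-minute trial with a day of two 10-puff collections and 12 hours of free use.
- The denominators take in subjects whose only exposure was the trial. A subject removed after A counts for A but never reaches B, C or D.

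What is at stake is how the by-product tolerability tables can be read, in a study meant to support a premarket application.

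**Working it through.** **Inputs.** Sequences ABDC, BCAD, CDBA and DACB (Protocol 5.3, SAP Table 2); 32 subjects (SAP 1.5); Day -1 order A, B, C, D with 10 minutes of use and about 30 minutes between trials (Protocol 5.1.2); nicotine strengths of 2.5, 4.0, 3.5 and 4.0% for A to D (SAP Table 1).

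**1. The plan's own figure.** 32 / 4 = 8 replications of each sequence, as SAP 1.5 states.

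**2. Balance on Days 1-4.** Across the four sequences each product takes positions 1, 2, 3 and 4 once, so its mean position is (1 + 2 + 3 + 4) / 4 = 2.5. Each of the 12 ordered pairs of neighbouring products occurs once. A design matrix with an intercept, 3 product columns and 3 position columns has rank 7 of 7, so product and position can be estimated separately.

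**3. Balance on Day -1.** With the single order A, B, C, D the same matrix has rank 4 of 7. The product and position columns are identical. This result needs no assumption about event rates or nicotine kinetics.

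**4. Timing.** Trials start at about 0, 40, 80 and 120 minutes. The last ends at 4 × 10 + 3 × 30 = 130 minutes. The strengths of the products already tried sum to 0 before A, 2.5 before B, 2.5 + 4.0 = 6.5 before C, and 6.5 + 3.5 = 10.0 before D. These sums describe what came before; they do not measure nicotine taken in.

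**5. Do Day -1 events reach the tables?** Events are recorded from consent (Protocol 8.1) and reviewed on Day -1 (Protocol 5.1.2). Any product use admits the subject to the Safety Population (Protocol 9.3, SAP 2.1.3). The product-emergent definition does not exclude Day -1, and the SAP 7.4 layout has no day or phase. Followed as written, it pools them.

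**6. Denominators.** If 32 subjects are randomised and *k* others are removed on Day -1 after using A, the denominator for A is 32 + *k*, while that for D can be as low as 32.

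**7. Illustration of size.** Assume no true product difference, a 10% event risk per product on Days 1-4, independence between phases, and every subject contributing to both. The pooled incidence is 1 - (1 - a)(1 - 0.10), where a is the Day -1 risk at that position. For D in the second row: 1 - 0.91 × 0.90 = 18.1%.

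| Assumed Day -1 risk, positions 1 to 4 | A | B | C | D | D minus A |
|---|---|---|---|---|---|
| 5, 5, 5, 5% | 14.5 | 14.5 | 14.5 | 14.5 | 0 |
| 3, 5, 7, 9% | 12.7 | 14.5 | 16.3 | 18.1 | +5.4 |
| 5, 10, 15, 20% | 14.5 | 19.0 | 23.5 | 28.0 | +13.5 |
| 9, 7, 5, 3% | 18.1 | 16.3 | 14.5 | 12.7 | -5.4 |

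The documents give none of these risks. The table shows only that the difference can be nil, positive or negative.

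**The case against.** **The general rule may already separate Day -1.** SAP 4.1 and Protocol 9.4 summarise by product and day, and SAP 7.4 never says that events are pooled over days. This is the strongest reply, and it makes the fault one of unclear layout rather than declared pooling. It does not settle the matter: SAP 4.1 yields to any other stated layout, and SAP 7.4 states one without day. Since onset date and time are recorded, the phase can be recovered.

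**The fixed order rests on one phrase.** The letters in brackets could simply name the products, and other sections speak only of an assigned schedule. But nothing describes orders that differ between subjects, and no randomised order exists at that time. A single order is the natural reading.

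**Nothing planned compares products on safety.** This stands. No objective concerns adverse events, Protocol 9.6 plans no formal safety tests, and the trial serves to accustom subjects and check tolerance.

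**Nothing shows that later products would be disadvantaged.** A reader might infer that accumulated nicotine would push events onto C and D. The documents do not establish this. Nausea, vomiting and dizziness did occur in an earlier repeated-use study. But throat irritation was the most common event in two of the three earlier pharmacokinetic studies (Protocol 1.2.2.1), and an irritant effect at first use would load A. The product-emergent definition does not recount under a later product an event that continues unchanged. No abstinence before check-in is stated, so nicotine load on arrival is uncontrolled.

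**Conclusion.** The point stands as a gap in SAP 7.4. Within Day -1 product and position are fully aliased, assuming the natural reading of Protocol 5.1.2. As written, the adverse event tables do not clearly exclude that phase or the subjects removed in it. In a pooled table the confounding is partial, because the Days 1-4 data are balanced. Its size and direction depend on how many events arise on Day -1 and cannot be derived from the documents. Only descriptive safety tables are touched; the sham-corrected primary analysis uses Days 1-4.

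Two stronger readings are not supported:

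- **That removals bias a product comparison.** A negative reaction to any product ends participation, so the triggering product does not change who continues. Disposition is summarised by sequence (SAP 5.0), not product. Protocol 4.5 classes subjects found ineligible before randomisation as screen failures, while the Safety Population wording keeps those who used a product. That bears on the denominators only.
- **That the trial order itself must be changed.** This would set a new exposure schedule for a tolerance check and need an IRB-approved amendment. The reporting problem can be solved without it.

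**What to change.** In SAP 7.4:

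1. Tabulate adverse events from the Day -1 product trial in a separate table by product. Give the number who tried each product, and add a note that product and trial position coincide. State which product an event arising between two trials is listed under; no rule now says.
2. Restrict the main by-product product-emergent tables to events with onset from first product use in each randomised period. Use as denominator the subjects who used that product on Days 1-4.

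The Safety Population need not change: subjects removed on Day -1 appear in the first table.

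The cost is a few lines of SAP wording, one extra table and slightly fewer events in the main tables. Onset date and time are already collected, so no new data and no protocol amendment are needed.
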